2.2 Rationale

Age Range

HPV testing is used in the screening algorithm of HIV-uninfected women age 30 or older. HPV testing has not been traditionally used for younger women because of the high-incidence of transient, insignificant HPV infections. However, HIV-infected young people have been noted to have a high prevalence of CIN2/3 as well as cases of invasive cancer. Therefore, the protocol team has opted to include younger women in this study.

Arm C

Women falling into either of the following two categories will be followed in Arm C: (i) women who have extensive cervical lesions that are inappropriate for cervical cryotherapy and (ii) high-risk HPV negative women with cervical lesions or a HSIL cytology. In a large screen-and-treat evaluation from Zambia, approximately 15% of women undergoing evaluation were thought to have lesions inappropriate for cryotherapy and were referred for LEEP [40]. In a recent presentation from Zambia, 20% of HIV-infected women had lesions inappropriate for cryotherapy. Of these women, 15%

had invasive cancer and another 33% had CIN2 or 3. Inclusion of this category of women in the present study will yield a larger number of participants for assessment of the HPV genotypes found in CIN2+ biopsy specimens (possible future study) and for the effect of LEEP on prevalent hr-HPV infections. In addition, these study populations will provide important data for implementation of the HPV test-and-treat strategy, as outlined in section 1.3.8, including the role of HPV testing in the management of women presenting with such conditions.

PEPFAR Objectives

Part of this study is being funded by a supplement from the U.S. NIH to conduct implementation science research of interest to the President's Emergency Plan for AIDS Relief (PEPFAR). The PEPFAR objectives in section 1.3.5 will use screening and baseline evaluations from all women who give consent for this study. The availability of the *careHPV* test should broaden access to cervical cancer screening through the HPV test-and-treat strategy. It will be critical to understand how this test performs in HIV-infected women. Although this assay has been conformité européenne (CE)-marked, it will not be widely available until late 2011. This study will compare *careHPV* results to two other HPV tests: HPV DNA PCR and aHPV. Cryotherapy is not recommended for women with extensive cervical lesions. Data from our Zambian investigators suggest that 15-20% of HIV-infected women will have such lesions and that half of these women will have CIN2/3 or invasive/microinvasive cancer on histology [40, 41]. Algorithms for cervical cancer screening must address treatment of these women to maximally impact mortality from cervical cancer.

Summary

An HPV test-and-treat strategy may become the standard of care for cervical cancer screening in resource limited settings because it is safe, effective, and inexpensive. A phase II study that randomizes women with hr-HPV was chosen because these women are at highest risk for CIN2+ and maximizes the efficiency of the study. Although limited data suggest an HPV test-and-treat strategy is effective in HIV-infected women, further study is needed before it can be broadly applied in this population. The protocol team proposes a proof-of-concept study in HIV-infected women to compare the effectiveness of immediate cryotherapy in women identified with high-risk HPV in screening to cytology-based strategy. It is imperative to understand how to apply an HPV test-and-treat strategy in HIV-infected women to reduce the morbidity and mortality due to cervical cancer.

3.0 STUDY DESIGN

A5282 is a randomized clinical trial of an HPV test-and-treat-strategy compared to cytology-based strategy. The study population is composed of HIV-1-infected women ages 18 years or older. No restrictions are in place for ART regimens, which will be initiated or continued according to the local standard of care. Sites should strongly consider initiating ART in women with a CD4 <350 cells/ μ L, if feasible. ART is not provided by the study. To be eligible, participants must have no history of cervical, vaginal, or vulvar cancer; no prior cervical cryotherapy, cervical conization, or hysterectomy; and no prior receipt of HPV vaccines.

The screening laboratory evaluations include CD4 cell count, plasma HIV-1 RNA viral load, and complete blood count. All participants will undergo a speculum examination at screening to obtain cervical specimens for cytology, aHPV, and HPV DNA PCR. Participants will be screened for hr-HPV with aHPV. This test semi-quantitatively detects the presence of type 16, type 18, or the presence of any of the other 12 types of hr-HPV (31, 33, 35, 39, 45, 51, 52, 56, 58, 59, 66, and 68). A separate specimen will be collected and stored for *careHPV* testing, which detects the 14 types listed above.

At screening, the examiner will also perform a visual inspection and colposcopy without biopsies to determine whether the candidate's cervix is suitable for cryotherapy. Participants with cervical lesions inappropriate for cryotherapy (as defined in Section 4.1.8) are not eligible for randomization but will be eligible to register to Arm C. Participants without hr-HPV (by aHPV) will also be eligible to register to Arm C if lesions were seen on the screening colposcopy or if the screening cytology shows HSIL.

The study will randomize 280 participants with hr-HPV (by aHPV) to Arm A or Arm B. Randomization will be stratified by current use of ART (i.e., any ART or no ART) with institutional balancing. Participants in Arm A (HPV test-and-treat) will undergo cervical cryotherapy at entry. Participants in Arm A will receive the results of the cytology, but participants will receive cryotherapy treatment regardless of the results. Participants in Arm B will follow a cytology-based management plan involving three steps – cytology, colposcopy with directed biopsies, and LEEP (as needed). Participants in Arms A and B will be seen at regular intervals post entry for aHPV, HPV DNA PCR, cervical cytology, and cervical colposcopy and directed biopsies for a total follow-up length of 130 weeks. A separate specimen will be collected 26 weeks post entry and stored for *careHPV* testing.

Participants in Arm C will undergo colposcopy and directed biopsies. If CIN2+ is found by biopsy, then LEEP will be performed and a follow-up visit 26 weeks after these procedures will be scheduled for aHPV, HPV DNA PCR, *careHPV*, cervical cytology, and cervical colposcopy and directed biopsies. After the week 26 visit, Arm C participants will go off study.

All participants undergoing cryotherapy or LEEP will be seen 4 weeks post-procedure to assess for AEs from the procedure. Quality assurance procedures are in place for reviews of digital impressions rendered during colposcopies (no lesions seen, lesions seen/appropriate for cryotherapy or lesions seen/not appropriate for cryotherapy). Slides from biopsies with and without CIN2+ will be reviewed regionally or centrally (see the A5282 Manual of Procedures [MOPS] for details). HPV DNA PCR and *careHPV* will be performed on stored specimens and results will not be used for clinical management.

4.0 SELECTION AND ENROLLMENT OF PARTICIPANTS

4.1 Inclusion Criteria

4.1.1 HIV-1 infection, documented by any licensed rapid HIV test or HIV enzyme or chemiluminescence immunoassay (E/CIA) test kit at any time prior to study entry

and confirmed by a licensed Western blot or a second antibody test by a method other than the initial rapid HIV and/or E/CIA, or by HIV-1 antigen, plasma HIV-1 RNA viral load.

NOTE: For sites located in countries other than the United States, the term "licensed" refers to a kit that has been certified or licensed by an oversight body within that country and validated internally.

World Health Organization (WHO) and Centers for Disease Control and Prevention (CDC) guidelines mandate that confirmation of the initial test result must use a test that is different from the one used for the initial assessment. A reactive initial rapid test should be confirmed by either another type of rapid assay or an E/CIA that is based on a different antigen preparation and/or different test principle (e.g., indirect versus competitive), or a Western blot or a plasma HIV-1 RNA viral load.

4.1.2 The following laboratory values obtained within 30 days prior to study entry:

- Absolute neutrophil count (ANC) $\geq 750/\text{mm}^3$
- Platelet count $\geq 75,000/\text{mm}^3$
- Hemoglobin (HgB) $> 8 \text{ gm/dL}$

4.1.3 For candidates suitable for cervical cryotherapy (as defined in section 4.1.8 below), hr-HPV detected by aHPV within 30 days prior to study entry.

NOTE: Participants with a visual inspection showing extensive lesions inappropriate for cryotherapy do not require an aHPV test result prior to enrollment.

4.1.4 For women without hr-HPV detected by aHPV, presence of lesions on visual inspection or HSIL cervical cytology.

4.1.5 Suitable candidate for cervical cryotherapy, defined as:

- No visible cervical lesions.
-- OR --
- Any visible lesions are located entirely on the ectocervix and are no more than 2 to 3 mm into the endocervical canal, AND
- visible lesions cover less than 75% of the cervix, AND
- all visible lesions are deemed appropriate for cryotherapy by the treating health care provider.

NOTE: Participants with cervical lesions inappropriate for cryotherapy are not eligible for randomization and should be followed in Arm C.

4.1.6 For participants of reproductive potential, negative serum or urine pregnancy test with a sensitivity of $<25 \text{ mIU/mL}$ within 48 hours prior to study entry.

NOTE: Reproductive potential is defined as women who have not been postmenopausal for at least 24 consecutive months (i.e., who have had

menses within the preceding 24 months) or women who have not undergone surgical sterilization (e.g., hysterectomy, bilateral oophorectomy, tubal ligation, or salpingectomy).

4.1.7 Contraception requirements

All study participants must agree not to participate in a conception process (e.g., active attempt to become pregnant or in vitro fertilization) from the time of study entry until 12 weeks after study entry.

If participating in sexual activity that could lead to pregnancy, the study participant must agree to use at least one reliable form of contraceptive from the time of study entry until 12 weeks after study entry. At least one of the following contraceptives MUST be used appropriately:

- Condoms (male or female) with or without a spermicidal agent
- Diaphragm or cervical cap with spermicide
- IUD
- Hormone-based contraceptive

NOTE: If participating in sexual activity that could lead to pregnancy, study participants taking efavirenz must use two forms of contraceptives.

Study participants who are not of reproductive potential (defined as women who have been postmenopausal for at least 24 consecutive months or have undergone surgical sterilization [e.g., hysterectomy, bilateral oophorectomy, or salpingectomy]) are eligible without requiring the use of contraceptives. Participant-reported history is acceptable documentation of sterilization, menopause, and a female's reproductive potential.

4.1.8 If recently gave birth, must be at least 12 weeks postpartum.

4.1.9 Females \geq 18 years of age at study entry.

4.1.10 Ability and willingness of participant or legal guardian/representative to provide written informed consent.

4.2 Exclusion Criteria

4.2.1 Current or prior history of cervical, vaginal, or vulvar cancer.

4.2.2 Prior cervical cryotherapy, LEEP, cervical conization, or total or partial hysterectomy.

4.2.3 Cervical, vaginal, or vulvar lesions that are suspicious on clinical exam for cancer.

4.2.4 Visual evidence of bacterial STIs or suspicion of pelvic inflammatory disease.

NOTE: Cervicitis or suspected pelvic inflammatory disease must be treated with appropriate antibiotics at least 7 days prior to entry.

- 4.2.5 Prior vaccination with an HPV vaccine.
- 4.2.6 Hemophilia.
- 4.2.7 Currently on anticoagulation therapy other than acetylsalicylic acid.
- 4.2.8 Serious illness requiring systemic treatment and/or hospitalization within 21 days prior to study entry.
- 4.2.9 Active drug or alcohol use or dependence or any other condition that, in the opinion of the site investigator, would interfere with the participant's ability to adhere to study requirements.

4.3 Study Enrollment Procedures

- 4.3.1 Prior to implementation of this protocol, and any subsequent full version amendments, each site must have the protocol and the protocol consent form(s) approved, as appropriate, by their local institutional review board (IRB)/ethics committee (EC) and any other applicable regulatory entity (RE). Upon receiving final approval, sites will submit all required protocol registration documents to the Division of AIDS (DAIDS) Protocol Registration Office (PRO) at the Regulatory Support Center (RSC). The DAIDS PRO will review the submitted protocol registration packet to ensure that all of the required documents have been received.

For studies at non-US sites, protocol activation is required prior to enrolling participants into the study.

Site-specific informed consent forms (ICFs) will be reviewed and approved by the DAIDS PRO, and sites will receive an Initial Registration Notification from the DAIDS PRO that indicates successful completion of the protocol registration process. A copy of the Initial Registration Notification should be retained in the site's regulatory files.

Upon receiving final IRB/EC and any other applicable RE approvals of an amendment, sites should implement the amendment immediately. Sites are required to submit an amendment registration packet to the DAIDS PRO at the RSC. The DAIDS PRO will review the submitted protocol registration packet to ensure that all the required documents have been received. Site-specific ICF(s) will not be reviewed and approved by the DAIDS PRO, and sites will receive an Amendment Registration Notification when the DAIDS PRO receives a complete registration packet. A copy of the Amendment Registration Notification should be retained in the site's regulatory files.

For additional information on the protocol registration process and specific documents required for initial and amendment registrations, refer to the current version of the DAIDS Protocol Registration Manual.

Once a candidate for study entry has been identified, details will be carefully discussed with the participant. The participant or legal guardian/representative will be asked to read and sign the approved ICF.

For participants from whom a signed ICF has been obtained, an ACTG Screening Checklist must be entered through the Data Management Center (DMC) Subject Enrollment System.

4.3.2 Randomization (Arms A and B)/Participant Registration (Arm C)

For participants from whom informed consent has been obtained, but who are deemed ineligible or who do not enroll into the initial protocol step, an ACTG Screening Failure Results form must be completed and keyed into the database.

4.4 Coenrollment Guidelines

Sites are strongly encouraged to coenroll participants in A5243, "Plan for Obtaining Human Biological Samples at Non-U.S. Clinical Research Sites for Currently Unspecified Genetic Analyses." Coenrollment in A5243 does not require permission from the A5282 protocol chairs.

Participants cannot be coenrolled in A5240, "A Phase II Study to Evaluate the Immunogenicity and Safety of a Quadrivalent Human Papillomavirus Vaccine in HIV-1-Infected Females."

Sites should consult the A5282 PSWP for other studies in which participants can be coenrolled, or contact the protocol chair and co-vice chairs via e-mail as described in the Study Management section for permission to enroll participants who are being followed in other clinical trials.

5.0 STUDY TREATMENT

5.1 Intervention, Administration, and Duration

5.1.1 Cervical Cryotherapy

Two 3-minute freezes separated by 5 minutes of thawing. Refer to the A5282 MOPS for a detailed description of this procedure.

5.1.2 LEEP

Refer to the A5282 MOPS for a detailed description of this procedure.

5.2 Study Product Formulation and Preparation

Not applicable.

5.3 Pharmacy: Product Supply, Distribution, and Accountability

Not applicable.

5.4 Concomitant Medications

5.4.1 Required Medications

If participating in sexual activity that could lead to pregnancy, participants must agree to use at least one reliable form of contraceptive (as defined in section 4.1.10) from the time of study entry until 12 weeks after study entry.

5.4.2 Prohibited Medications

None.

5.4.3 Precautionary Medications

Participants who require anticoagulation medication other than acetylsalicylic acid should not undergo cervical biopsies, LEEP, or cryotherapy.

Site investigators are encouraged, but not required, to delay HPV vaccinations for participants in Arms A and B until 24 weeks post entry.

6.0 CLINICAL AND LABORATORY EVALUATIONS

6.1 Schedule of Events

Evaluation	Screening	Entry (day 0)	Post Entry Evaluations					4 weeks post cervical treatment
			Week 26 (Final Visit for Arm C)	Week 52	Week 78	Week 104	Week 130 (Final Visit for Arms A and B) / Disc Evals	
Documentation of HIV-1	X							
Medical history / Medication history	X							
Nadir CD4 cell count	X							
Complete physical examination (PE)	X							
Clinical assessments	X	X	X	X	X	X	X	
Hematology	X							
Pregnancy test	within 48 hours prior to entry		whenever suspected, prior to cryotherapy and prior to LEEP					
CD4 cell count	X							
Plasma HIV-1 RNA	X							
Speculum examination and colposcopy	X							
Real-time aHPV and Stored HPV DNA PCR	X							
Stored aHPV and Stored HPV DNA PCR			X	X	X	X	X	
Stored careHPV	X		X					
Cervical cytology	X		X	X	X	X	X	
Colposcopy and directed biopsies		See Section 6.3.10	X		X		X	
LEEP			only if CIN2+ is found on biopsy					
Cryotherapy (Arm A only)		X						
Assessment of targeted AEs		X						X
Sociodemographic and sexual behavior questionnaire		X	X	X	X	X	X	

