Part of this study is being funded by a supplement from the U.S. NIH to conduct implementation science research of interest to the President’s Emergency Plan for AIDS Relief (PEPFAR). The PEPFAR objectives in section 1.3 will use screening and baseline evaluations from all women who give consent for this study. The availability of the **xpert hrHPV** ~~careHPV~~ test should broaden access to cervical cancer screening through the HPV test-and-treat strategy. It will be critical to understand how this test performs in HIV-infected women. ~~Although this assay has been conformité européenne (CE) marked, it will not be widely available until late 2011.~~ This study will compare **xpert hrHPV** ~~careHPV~~ results to two other HPV tests: HPV DNA PCR and aHPV. Cryotherapy is not recommended for women with extensive cervical lesions. Data from our Zambian investigators suggest that 15-20% of HIV-infected women will have such lesions and that half of these women will have CIN2/3 or invasive/microinvasive cancer on histology [40, 41]. Algorithms for cervical cancer screening must address treatment of these women to maximally impact mortality from cervical cancer.

2. Per the March 2015 interim DSMB review, biopsies are being added to study follow-up visits for all participants, regardless of preceding colposcopy results.

- Section 3.0, fourth paragraph, now reads: Participants in Arms A and B will be seen at regular intervals post entry for aHPV, HPV DNA PCR, cervical cytology, and cervical colposcopy and directed biopsies for a total follow-up length of 130 weeks. **At least two cervical biopsies should be performed at the week 78 and week 130 visits. Visible lesions should be biopsied preferentially. If no visible lesions are seen, then two random biopsies should be obtained.**
- Section 6.3.10, subsection on colposcopy and directed biopsies, now reads:

Post entry:

- Participants in Arms A and B will undergo colposcopy and directed biopsies at the weeks 26, 78, and 130 clinic visits. **At least two cervical biopsies should be performed at the week 78 and week 130 visits. Visible lesions should be biopsied preferentially. If no visible lesions are seen, then two random biopsies should be obtained.**
- Participants in Arm C who undergo LEEP post-entry will undergo colposcopy

and directed biopsies at the week 26 clinic visit.

Digital images and colposcopic impression will be submitted for review, along with location of cervical biopsies.

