(The following paragraph supersedes Clarification Memo [CM] #2, dated 01/02/1014.) Directed biopsies will be obtained from areas suspicious for CIN. ~~Biopsies are taken only if lesions are seen upon colposcopy.~~ In the event lesions are not seen upon colposcopy but the cytology specimens show presence of HSIL, then the participant should return to the study clinic for repeat colposcopy and other diagnostics procedures such as endocervical curettage (ECC), random cervical biopsies (**if not already done**), or diagnostic LEEP. Results of these diagnostic tests must be recorded on the appropriate CRF. ~~Slides from biopsies of CIN2+ and biopsies without CIN2+ will be submitted for review.~~ If CIN2+ is detected by biopsy, the participant will undergo LEEP.

- c. Sample Informed Consent, What do I have to do if I am in this Study?, Groups A and B: At the study visit about 6, 18, and 30 months after the entry visit you will also have a colposcopy and biopsies if any abnormal areas are seen. **At months 18 and 30, you will have two biopsies performed whether or not abnormal areas are seen.**

3. Additional clarifications were made to Section 6.3.10.

- a. The subsection, "Diagnoses," now reads:

Diagnoses

(Per CM #1, dated 02/05/1013.) After entry, record any new diagnoses made since the last visit using the ACTG criteria for clinical events and other diseases.

(Per CM #1, dated 02/05/1013.) Except for invasive cancer, cervical cytology and histology results do not need to be recorded as events; these results will be entered on study-specific CRFs only.

(New language) Record all histology results from procedures for the diagnosis or treatment of cervical HSIL (such as cervical conization or hysterectomy) and from biopsies performed related to the presence or absence of squamous intraepithelial lesions on the appropriate CRFs.

- b. The subsection, "LEEP," now reads:

(The following paragraph supersedes item 4b in LoA #2, dated 08/09/1012.)

LEEP

Participants found to have CIN2+ by biopsy at any point during the study will be offered LEEP **or other excisional treatment** (except for participants in Arm A **prior to week 26** who have CIN2+ on pre-cryotherapy biopsy at entry). If the participant had a prior LEEP, treatment of recurrent **or incompletely treated**

CIN2+ is at the discretion of the site investigator. These participants will continue on study.

(No changes to the remainder of this subsection.)

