A Limited Center Trial of the AIDS Clinical Trials Group (ACTG)

DAIDS ES # 10845

Letter of Amendment Date: 9 August 2012

ACTG Network Coordinating Center

Social & Scientific Systems, Inc.
[name]
[name] 20910

[contact]
[contact]

LETTER OF AMENDMENT

DATE: August 9, 2012

TO: Non-US ACTG CTU Principal Investigators, CRS Leaders, and CTU/CRS Coordinators Participating in the A5282 Study

FROM: A5282 Protocol Team

SUBJECT: Letter of Amendment #2 for Protocol A5282, Version 1.0, 11/16/2010, entitled "A Randomized, Phase II Trial to Compare an HPV Test-and-Treat Strategy to a Cytology-based Strategy for Prevention of CIN 2+ in HIV-infected Women"

The following information impacts the A5282 study and must be forwarded to your institutional review board (IRB)/ethics committee (EC) as soon as possible for their information and review. This must be approved by your IRB/EC before implementation.

[figure not shown]
The following information may also impact the Sample Informed Consent. Your IRB/EC will be responsible for determining the process of informing subjects of the contents of this Letter of Amendment (LOA).

Upon receiving final IRB/EC and any other applicable regulatory entity approvals for this LOA, sites should implement the LOA immediately. Sites are still required to submit a LOA registration packet to the DAIDS Protocol Registration Office (PRO) at the Regulatory Support Center. Sites will receive a registration notification for the LOA once the DAIDS

PRO verifies that all the required LOA registration documents have been received and are complete. An LOA registration notification from the DAIDS PRO is not required prior to implementing the LOA. A copy of the LOA registration notification along with this letter and any IRB/EC correspondence should be retained in the site's regulatory files.

The following are changes to A5282, Version 1.0, 11/16/2010:

1. Figure 1, Overview of Study Design

2. Clarification of contraception requirements if using Efavirenz (EFV)

a. Section 4.1.7, Contraception Requirements

NOTES: If participating in sexual activity that could lead to pregnancy, study participants taking **efavirenz should conform to local or WHO guidelines regarding prevention of pregnancy while on efavirenz.**

b. Sample Informed Consent, "What do I need to know about pregnancy and contraceptives?"

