6.3.7 Laboratory Evaluations

At screening, entry, and post entry record all Grade ≥ 3 laboratory values.

Hematology

ANC, platelet count, and HgB.

Pregnancy Test

For women with reproductive potential, a negative serum or urine β -HCG (urine test must have a sensitivity of <25 mIU/mL) pregnancy test must be performed within 48 hours prior to study entry, prior to cryotherapy and LEEP (if done), and post entry whenever pregnancy is suspected. (See section 7.4 for the management of study participants who become pregnant after entry.)

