6.3.10 Other Laboratory Studies and Procedures

Refer to the A5282 MOPS for detailed instructions on how to perform colposcopy and biopsies, collect specimens for aHPV, HPV DNA PCR, and *careHPV*, perform cervical cytology, cryotherapy, and LEEP, and detailed plans for the quality assurance of clinical procedures.

Participants must refrain from any kind of sexual activity, douching, and inserting any intravaginal products for at least 48 hours prior to the collection of vaginal/cervical specimens.

Speculum Examination and Colposcopy

Participants will undergo a speculum examination at screening to obtain cervical specimens for HPV testing and cytology. If participants have visual evidence of bacterial STIs or an examination consistent with pelvic inflammatory disease, then samples for HPV testing and cytology should not be obtained. Instead, these women should be treated according to the local standard of care, in which case screening evaluations can be performed a minimum of 7 days after initiating treatment.

A trained examiner will also perform colposcopy at screening to determine whether the participant's cervix is suitable for cryotherapy and for visual impression only. Digital images will be taken using a video colposcope provided to sites by the study, and submitted for review along with the colposcopic impression provided by the examiner as to the degree of CIN (no lesions seen, lesions seen appropriate for cryotherapy, lesions seen not appropriate for cryotherapy). Refer to the A5282 MOPS for detailed procedures.

No biopsies are to be obtained at screening unless the examiner is suspicious of invasive cervical, vaginal, or vulvar cancer, in which case the participant will not be enrolled into the study and will be managed as per section 7.3.

aHPV

A cervical specimen will be obtained at screening for real-time aHPV testing. Post-entry, specimens will be obtained for aHPV and stored locally (refer to the A5282 MOPS).

HPV DNA PCR

Specimens will be stored for HPV DNA PCR. Testing will be performed on the same specimen as the aHPV. Specimens may be shipped to the U.S. for HPV typing at a central laboratory, if permitted by in-country regulations, or batch tested at a local or regional laboratory. Specimens obtained by LEEP will also be stored locally for possible future testing by HPV DNA PCR.

careHPV

A cervical cytobrush specimen will be obtained for *careHPV* and stored locally in the appropriate media (refer to the A5282 MOPS).

Cytology

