7.4 Pregnancy

Participants who become pregnant after study entry will continue to be followed on study. These participants will come into the clinic to complete study evaluations as per the schedule in Section 6.1 but will not undergo LEEP, cryotherapy, or cervical biopsy until 6 weeks after the pregnancy is completed. If there is suspicion of invasive cancer, clinical management is left to the discretion of the site investigator.

Pregnancy outcome for the participant and the infant will be recorded on a CRF at the end of the pregnancy.

If pregnancy occurs for a participant on study who is on ARVs, sites are strongly encouraged to register the pregnancy with The Antiretroviral Pregnancy Registry as soon as the site becomes aware of it. More information is available at www.apregistry.com.

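### Section 7.4 defers cervical biopsy in pregnancy, but Sections 6.1 and 6.3.7 require a pregnancy test only before LEEP and cryotherapy, so an unsuspected pregnancy can be biopsied at weeks 78 and 130

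*Protocol*

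**What the plan says.** **Who waits.** Protocol Section 7.4 keeps women who become pregnant on study and on the visit schedule, "but will not undergo LEEP, cryotherapy, or cervical biopsy until 6 weeks after the pregnancy is completed".

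**Who is tested.** Section 6.1 calls for a test within 48 hours before entry and, after entry, "whenever suspected, prior to cryotherapy and prior to LEEP". Section 6.3.7 repeats this for women with reproductive potential: "prior to cryotherapy and LEEP (if done), and post entry whenever pregnancy is suspected".

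**Who is biopsied.** The Letter of Amendment that followed the March 2015 DSMB review (item 2, changing Sections 3.0 and 6.3.10) requires at least two biopsies at weeks 78 and 130 in Arms A and B. It adds: "If no visible lesions are seen, then two random biopsies should be obtained". The matching consent text reads "At months 18 and 30, you will have two biopsies performed whether or not abnormal areas are seen".

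**Contraception.** Section 4.1.7 requires "at least one reliable form of contraceptive from the time of study entry until 12 weeks after study entry". Under Letter of Amendment #2, women on efavirenz "should conform to local or WHO guidelines regarding prevention of pregnancy while on efavirenz".

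**Procedure detail.** Section 6.3.10 sends sites to a manual that is not among the documents: "Refer to the A5282 MOPS for detailed instructions on how to perform colposcopy and biopsies".

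**The concern.** Section 7.4 names three procedures that must wait, and the testing rules cover two of them. For LEEP and cryotherapy the protocol does not rely on suspicion; it requires a test. For biopsy it relies on suspicion alone, which by definition cannot find an unsuspected pregnancy.

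This mattered less when follow-up biopsies were taken mainly from visible lesions. Once biopsy became routine at weeks 78 and 130, every woman attending was to have the procedure, long after required contraception had ended for most of them. At stake is participant safety under the protocol's own rule: a site could comply fully with Sections 6.1 and 6.3.7 and still do what Section 7.4 says should be deferred.

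**Working it through.** The plan gives no pregnancy rate, so there is no plan figure to reproduce. Steps 1 to 3 compare text. Steps 4 to 6 are arithmetic, partly on assumptions.

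**1. Sections side by side**

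| Procedure | Deferred in pregnancy (7.4) | Test required before it (6.1, 6.3.7) |
|---|---|---|
| LEEP | Yes | Yes |
| Cryotherapy | Yes | Yes |
| Cervical biopsy | Yes | No; only if pregnancy is suspected |

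**2. Do the other triggers reach the week 78 and 130 biopsies?** No.
- The 48-hour test belongs to entry.
- Study cryotherapy is given only in Arm A, at entry.
- LEEP follows a CIN2+ biopsy result, so its test comes after the biopsy.
- The general contraception requirement ended 78 - 12 = 66 weeks before the week 78 visit and 130 - 12 = 118 weeks before the week 130 visit.

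**3. Does any amendment close the gap?** No. The post-March-2015 letter changes Sections 3.0, 6.3.10 and 7.3 and the consent, but not the pregnancy-test row, Section 6.3.7 or Section 7.4. Letters #1 and #2 and Clarification Memos #1 and #2 add no pre-biopsy test.

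**4. Size**

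From the protocol (9.4): 280 randomised and up to 20% lost, so 280 x 0.8 = 224 women.

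Assumed, not in the documents: 5 to 10 pregnancies per 100 woman-years; 3 to 6 weeks unrecognised; 70% to 90% of reproductive potential.

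Chance that a woman of reproductive potential has an unrecognised pregnancy at a given visit = rate x weeks / 52:
- low: 0.05 x 3/52 = 0.288%
- high: 0.10 x 6/52 = 1.154%

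This is one such pregnancy per 1/0.01154 = 87 to 1/0.00288 = 347 women tested.

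If each of the 224 women has one mandatory biopsy visit after the amendment:
- low: 224 x 0.00288 x 0.7 = 0.45
- high: 224 x 0.01154 x 0.9 = 2.33

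If only half of them have such a visit, both halve: 0.45 x 0.5 = 0.23 and 2.33 x 0.5 = 1.16.

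A test also misses the earliest pregnancies. If the first week is undetectable (assumed), testing at one visit per woman would find 224 x 0.05 x 2/52 x 0.7 = 0.30 to 224 x 0.10 x 5/52 x 0.9 = 1.94.

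**5. Who still had a mandatory biopsy to come?** Accrual dates are not given. On the planned 15 months (9.4), counted from the version date of November 2010 because the release date is not given, accrual ends in February 2012. The last week 130 visit would then be about August 2014, before the March 2015 review. For the amendment to reach anyone, accrual must have run later than planned, by an unknown amount.

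**6. Delay once a pregnancy is found.** Assume it is found at 4 to 10 weeks and carried to 40. The delay is (40 - 10) + 6 = 36 to (40 - 4) + 6 = 42 weeks.
- From week 78: 78 + 36 = 114 to 78 + 42 = 120. The week 78 window (6.2.3, +/- 6 weeks) closes at 84.
- From week 130: 130 + 36 = 166 to 130 + 42 = 172. The final-visit window (+/- 12 weeks) closes at 142.

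**The case against.** **Section 7.4 is a management rule for known pregnancies.** It sets no standard for detecting them. The text can be read as tiered: mandatory tests before treatment, suspicion-based tests before diagnostic sampling. This stands to the extent that a reader who infers a contradiction between the sections goes too far. What remains is a gap in carrying out Section 7.4, which itself puts biopsy alongside the two treatments, as Section 5.4.3 does for anticoagulation.

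**Harm is not shown.** This stands. The risk list in Section 2.1 gives only a possible increase in miscarriage after multiple biopsies, under rare risks, and does not say that it concerns biopsy during pregnancy. A reader might infer that these biopsies endanger early pregnancies; the documents do not establish that.

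**Other sources may already require a test.** The manual of procedures or the removed consent pages may do so, and neither can be seen. That would protect participants, but it would not change what Sections 6.1 and 6.3.7 say.

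**Safeguards exist.** Clinical assessments and the sexual behaviour questionnaire at every scheduled visit can raise suspicion. Miscarriages go to expedited reporting (11.4.2), pregnancy outcomes are recorded (7.4) and the DSMB reviews adverse events (9.5). The first two narrow the gap to early, unsuspected pregnancies. The others would capture a signal but do not prevent exposure.

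**The count is easy to inflate.** A reader might charge all 224 women with both mandatory visits. That needs every woman to reach week 78 after March 2015, hence to have entered after about September 2013, nearly three years after Version 1.0. Nothing visible supports this. Women past week 78 at the amendment count at most once, and women past week 130 not at all.

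**Conclusion.** The gap is in the current text: three procedures are deferred in pregnancy, two have a mandatory test, and the third became routine at weeks 78 and 130 without a change to the testing rules. It is a minor safety point with a cheap remedy.

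Its size is a few exposures at most: about 0.5 to 2.3 if every retained woman had one mandatory biopsy visit after the amendment, and 0.2 to 1.2 if half did. The pregnancy rate, the unrecognised interval and the share of women of reproductive potential are outside assumptions, and the number of visits after the amendment is unknown. The conclusion rests on Section 7.4 and not on these counts. It does not touch the endpoint definition, power or inference.

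**What to change.** Add *prior to cervical biopsy* to the pregnancy-test row in Section 6.1 and to the pregnancy-test paragraph in Section 6.3.7, for women of reproductive potential as defined in the note to Section 4.1.6. The tested procedures then match those deferred in Section 7.4. If the manual of procedures or the consent already requires the test, state it in these two sections as well.

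**Cost in tests.** One urine test before each biopsy, at visits already scheduled: 224 x 0.7 = 157 to 224 x 0.9 = 202 per mandatory visit if all 224 women still have that visit to come. Biopsies at week 26, when a lesion is seen, and unscheduled biopsies add some.

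**Cost in data.** For the few women found pregnant, the week 78 biopsy is missed or done well outside its window, so a CIN2+ diagnosis could come later. At week 130 the final biopsy would usually be missing. Such a woman, if still event-free, would be censored at her last visit with a biopsy result (Protocol 9.6.1) or, under SAP Section 3, at the latest of her last biopsy, colposcopy or Pap smear. Section 7.4 already accepts this loss for any recognised pregnancy.
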